### 5.3. Data Collection

An investigator at each contributing hospital will be appointed to be responsible for data collection of all appropriate patients. Patients for AP may be admitted under multiple teams, it is the hospital lead's responsibility to capture all patients with AP that occur during the study inclusion period.

Data will be collected and stored using the web application REDCap. This web application is encrypted with HIPAA-Security, compliant with guidelines in the United States, and is widely used by academic institutions.

REDCap is a secure, web-based software platform designed to support data capture for research studies. It provides: 1) an intuitive interface for validated data capture; 2) audit trails for tracking data manipulation and export procedures; 3) automated export procedures for seamless data downloads to common statistical packages; and 4) procedures for data integration and interoperability with external sources.

Clinical data at each participating hospital will only be accessed by medical students and resident medical officers who already have access to the clinical data being collected. Individuals working at other centres, and those without access to patient clinical data, will not be involved in data collection. Locality approval will be sought and obtained at all centres prior to study commencement. An excel spreadsheet will be kept alongside the REDCap database at each hospital. This will be stored on a password protected hospital computer at each hospital. A unique RedCap number will be created for each patient. This number will allow re-identification of patients by the local hospital lead if required. After data has been uploaded into REDCap the local hospital copy of the data will be destroyed to protect patient privacy. An excel spreadsheet containing the REDCap key and the relevant patients NHI will be kept. This excel spreadsheet will allow future patient re-identification if required. During REDCap data upload there will be no data fields where identifiable data can be uploaded; for example, names or NHI's. Local excel files will be stored at each hospital for 10 years and destroyed following this. The central de-identified data set will be stored for 10 years using REDCap electronic data capture tools.

If further studies using this data set are to be performed a subsequent ethics application will be required before its use.

All hospital leads will also be required to complete a hospital-survey which assess hospital-related variables (*Appendix C*).

Data collection will occur at two timepoints. The first time point will be within or at 48 hours of admission to hospital and secondly at 30-days follow-up following admission to the emergency department .

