## Study Timeline

Dates	Description
10 February 2024	
 
● Preliminary protocol drafted
 
● Quality performance indicators finalised
 

March 21 2024	
 
● HDEC submission (expedited pathway) in
 
● Tupu grant application in
 

March 27 2024	
 
● Data collection form finalised/ redcap form created
 

April (first week) 2024	
 
● Second general meeting of investigators and protocol finalised
 
● Slide made for NZAGS conference and presented
 
● REDCap users generated and sent to investigators
 

April - June 2024	Centres recruited and locality ethics applications in 
 
● Prepare for data collection
 

01 July 2024	Data upload window opens
30 September 2024	Data upload window ends - REDCap locked for new entries
31 October 2024	30-day follow up from day of admission
November/December 2024-January 2025	Data analysis and manuscript writing

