Type of opioid prescribed (if any)	Codeine/ Morphine/ Fentanyl/ Tramadol/ Oxycodone/ Other (please specify)/ no opioids prescribed
Date opioid analgesia first administered	Date (dd/mm/yyyy)
Time opioid medication is administered to patient	24 hour clock
Route	PO/ IV
(If regular) daily dose	mg
(If PRN) total dose in first 72 hours	mg

(If yes) Date opioids first administered	Date (dd/mm/yyyy)
(If yes) Time opioid medication first administered as per drug chart?	24 hour clock
Further analgesic modalities	PCA/ ketamine/ local nerve blocks/ other (please specify)
Transfer to different hospital	
Patients with predicted severe disease discussed with specialised pancreas service ( Appendix B ) in first 72 hours from admission	Yes/ No/ not applicable
Patient transferred to a different hospital in the first 72 hours?	Yes/No
(If yes) Date of transfer	Yes/No
(If yes) Location transferred to	List of hospitals
(If yes) Reason for transfer to different hospital?	Severe disease/ requires ERCP/ requires interventional management of local complication/ other (free text)
ERCP	
Cholangitis in first 72 hours ( Appendix F )	Yes/ No
Cholestasis in first 72 hours (radiological + deranged LFTs)	Yes/ No
ERCP performed in the first 72 hours	Yes/ No
Fluid management*	
Baseline variables	
Bag 1	
Date of administration	Date (dd/mm/yyyy)
Time of administration	Time (24-hour)
Volume administered	Volume (ml)
How long does fluid run for?	Time (hours)
Type of fluid	0.9% Normal saline/ Hartmann's/ plasmalyte/ colloid/ 0.45 saline + dextrose/ 0.18 saline + dextrose/ other (please specify)
Further administration of intravenous fluid (IVF) in the first 3 days of admission? ( Appendix B )	Yes/no
Bag 2	
Date of administration	Date (dd/mm/yyyy)
Time of administration	Time (24-hour)

Volume administered	Volume (ml)
Time fluid is administered	Time (hours)
Type of fluid	0.9% Normal saline/ Hartmann's/ plasmalyte/ colloid/ other (please specify)
Further administration of intravenous fluid (IVF) in the first 2 days of admission?	Yes/no
Documented fluid review after 12 hours ( $\pm$ 4 hours)	Yes/no
Documented fluid review after 24 hours ( $\pm$ 4 hours)	Yes/no
Documented fluid review after 48 hours ( $\pm$ 4 hours)	Yes/no
Documented fluid review after 72 hours ( $\pm$ 4 hours)	Yes/no
Early Nutritional support	
On admission patient kept nil by mouth (NBM)	Yes/no

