## 5.6. Follow-up

All patients will be followed for the initial 72 hours following admission into ED by a clinician and then again chart reviewed at 30 days from initial admission.

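### Section 5.3 sets the first data capture at or before 48 hours, but Section 5.6, the primary aim and 17 data fields run to 72 hours; no text says when the 72-hour items are completed

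*Protocol*

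**What the plan says.** Section 5.3 (Data Collection) provides for two captures. Of the early one it says: "The first time point will be within or at 48 hours of admission to hospital". It puts the later one at 30 days, counted from emergency department admission.

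Section 5.6 (Follow-up) says instead: "All patients will be followed for the initial 72 hours following admission into ED by a clinician and then again chart reviewed at 30 days".

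Section 2 (Aims) and the Study Summary define the care being measured as the first 72 hours. In Table 1 (Section 3), specialist discussion (QPI 6) and the start of enteral nutrition (QPI 11) run to 72 hours, the fluid metrics (QPI 8) include the third 24 hours, and the CT indicator (QPI 5) refers to 72–96 hours.

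Section 5.5 (Required data) asks many items over 72 hours, among them "Documented fluid review after 72 hours", with a tolerance of ±4 hours. In the fluid section, the follow-on question after bag 1 covers 3 days. After bag 2 it reads "Further administration of intravenous fluid (IVF) in the first 2 days of admission". The table's footnote gives 72 hours.

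The Study Timeline has for 30 September: "Data upload window ends - REDCap locked for new entries". It places 30-day follow-up at 31 October.

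**The concern.** Both timings cannot govern the same early form. At 48 hours a collector cannot know whether the patient will tolerate oral intake by 72 hours, have a fluid review at 72 hours, or have a CT, antibiotics, enteral or parenteral feeding, or a specialist discussion during the third day. A negative answer given then is provisional, and nothing in the protocol marks it so.

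The primary outcome is overall QPI compliance, and Section 8 compares hospitals on funnel plots. If some sites work to 5.3 and others to 5.6, they observe different lengths of care, and the difference could appear as variation in practice. Adjustment for patient risk would not remove it. Multiple imputation would not either, because a provisional No is not a missing value.

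The bag 2 wording is a related problem. Each Yes opens the next bag, so a collector who takes the 2-day wording literally can answer No for a patient whose next bag is on day 3, and the record stops there. That can happen however late the form is completed.

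**Working it through.** The protocol gives no figure to reproduce. The check is a side-by-side reading, a count, and an illustration.

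**1. Stated timings**

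| Place | Timing |
|---|---|
| 5.3, first capture | at or before 48 h |
| 5.6, early follow-up | 72 h |
| Section 2, care being measured | 72 h |
| Table 1, QPIs 6 and 11; QPI 8 metrics | 72 h |
| Table 1, QPI 5 | 72–96 h |
| 5.5, 72-hour fluid review | 72 ± 4 h, so up to 76 h |
| 5.5, further fluid: bag 1 / bag 2 / footnote | 3 days / 2 days / 72 h |

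**2. Fields in 5.5 whose window reaches 72 hours**

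- Aetiology, severity, imaging, antibiotics: alcohol history, triglycerides, predicted severity, CT performed, CT indication, antibiotics = 6.
- Analgesia, transfer, ERCP, fluids: as-required opioid dose, specialist discussion, transfer, cholangitis, cholestasis, ERCP, 72-hour fluid review, further fluid after bag 1 = 8.
- Nutrition: oral intake by 72 hours, enteral feeding, parenteral feeding = 3.

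Total 6 + 8 + 3 = 17, of which 16 are worded as 72 hours and one as 3 days. A 48-hour capture leaves (72 − 48)/72 = 33% of the elapsed window still to come.

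**3. Which of the 17 bear on a QPI that is still open after 48 hours**

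- QPI closes by 48 hours (7 fields): alcohol and triglycerides (QPI 2, 24 hours), predicted severity (QPI 3, on admission, although it also helps define who qualifies for QPI 6), opioid dose (QPI 7, one hour), and cholangitis, cholestasis and ERCP (QPI 12, 48 hours).
- Exposed (8 fields): CT performed and its indication (QPI 5), specialist discussion and transfer (QPI 6), further fluid (QPI 8 metrics), antibiotics (QPI 10), enteral and parenteral feeding (QPI 11).
- No QPI is decided by the field (2): 72-hour fluid review, oral intake by 72 hours.

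7 + 8 + 2 = 17.

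**4. Direction and possible size**

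Let p be true compliance, q the share of the relevant events falling at 48–72 hours, and r the share of those not back-filled. The protocol gives none of the three; the values below are assumptions.

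For an item that should be done by 72 hours (specialist discussion, enteral nutrition), recorded compliance = p(1 − qr). With p = 70%:

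| q | full back-fill (r = 0) | half (r = 0.5) | none (r = 1) |
|---|---|---|---|
| 10% | 70% | 66.5% | 63.0% |
| 20% | 70% | 63.0% | 56.0% |

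For an item that should be avoided (prophylactic antibiotics, early CT without a listed reason, parenteral nutrition), the missed events are breaches, so recorded compliance = 1 − (1 − p)(1 − qr). With p = 70% and r = 1, this is 1 − 0.30 × 0.90 = 73% for q = 10% and 1 − 0.30 × 0.80 = 76% for q = 20%.

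**5. The REDCap lock**

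Enrolment runs 1 July to 30 September: 31 + 31 + 30 = 92 days. If a site creates the record only once 72 hours have passed, patients admitted on 28, 29 and 30 September fall after the lock: 3/92 = 3.3% of enrolment days. If the record is created on the day of admission, the loss is zero.

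**The case against.** The strongest reply is that this is a chart-based study with a second look. Section 5.6 already provides for 72 hours of follow-up and a chart review at 30 days. Section 6.1 says follow-up data come from routine notes, and Sections 5.3 and 6.3 keep a key linking each REDCap record to the patient. Third-day events can therefore still be found.

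This stands in part. A reader might infer that third-day events will be recorded as not done. The protocol does not support that: it does not say that the early form closes at 48 hours, that an open item is coded No, or that the 30-day review may not complete it. Equally, it does not say that the 30-day review does complete it. The headings in 5.5 that refer to 30 days cover local complications, organ failure and other outcomes, and no process-of-care item is assigned to that review.

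It can also be said that the count of 17 overstates the reach. That is right: seven of the fields serve QPIs that close by 48 hours. For example, an ERCP on the third day would not meet QPI 12 in any case. The 33% is elapsed time and should not be read as a share of events.

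On the lock, the timeline bars new entries, not editing of existing records, so 3 of 92 days is a conditional upper bound and not an expected loss. On bag 2, the footnote does give 72 hours for later bags. That shows the likely intent, but it leaves the question itself worded differently.

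**Conclusion.** The internal contradiction stands. Section 5.3 sets the early capture at or before 48 hours, against 72 hours of follow-up in 5.6, a 72-hour primary aim and 17 fields that reach 72 hours or 3 days. The bag 2 question contradicts both bag 1 and the footnote.

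The consequence is a risk that depends on two conditions: that sites complete the form at 48 hours as written, and that the open items are not completed later. Under both, compliance would be understated for specialist discussion and enteral nutrition and overstated for antibiotics, early CT and parenteral nutrition, and the third-24-hour fluid metrics would be incomplete. The errors run in opposite directions, so the net effect on overall compliance cannot be signed. Its size is unknown and could be zero; the figures of 56–63% and 73–76% against a true 70% rest wholly on assumed event timing and no back-fill. That sites would differ on the funnel plots is possible, not shown.

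**What to change.** - Reconcile 5.3 with 5.6. State that the early form is completed by chart review after the 72-hour window has closed, including the 4-hour tolerance for the 72-hour fluid review (so not before 76 hours), or at discharge or death if earlier.
- Reword the bag 2 follow-on question to the first 72 hours, matching bag 1 and the footnote, and carry this through to later bags.
- State that for patients admitted up to 30 September, records may be created, or existing ones completed, after the 30 September lock until their early data are entered. This belongs with the first change, because asking sites to wait makes late record creation more likely.

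A form completed at 76 hours still does not cover the 72–96 hours named in QPI 5. The CT field in 5.5 asks only about the first 72 hours, so the authors should confirm that this is the window they intend to score.

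The cost is a few wording changes and an exception to the lock for the last admissions. No extra visits or patient contact are needed, since all the data come from routine notes.

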### 5.4. Patient eligibility

#### *Inclusion Criteria*

- All patients  $\geq 16$  years old who present with AP, as defined by the revised Atlanta criteria (*Appendix B*)
- Presenting to a public hospital that manages acute patients in AoNZ.

#### *Exclusion Criteria*

- Age less than 16
- Chronic pancreatitis (*Appendix B*)
- Patients with suspected respiratory distress ( $SpO_2/FiO_2 \leq 315$ ) who did not have an arterial blood gas test done to confirm respiratory failure.
- Postoperative pancreatitis following upper gastrointestinal surgery (not including endoscopic retrograde cholangiopancreatography [ERCP])

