## Study Summary

Study title	An Aotearoa-New Zealand (AoNZ) multi-centre, prospective cohort study of acute pancreatitis management and outcomes.
Internal ref. no./ short title	PANORAMA Study
Study design	Multicentre prospective observational cohort study.
Study population	Adult patients diagnosed with acute pancreatitis admitted to any public hospital in AoNZ.
Eligible centres	All public hospitals in AoNZ.
Planned cohort	Enrolment for 3 months.
Objective	To measure adherence to quality performance indicators of the early (<72 hours) management of acute pancreatitis (AP) in AoNZ.
Primary outcomes of interest	
 
• Proportion of patients that were managed in compliance with quality performance indicators overall
 

Secondary outcomes of interest	
 
• Variation in compliance with QPIs between hospitals for each of the management domains
 
• Requirement for mechanical ventilation (invasive and non-invasive)
 
• Requirement for renal replacement therapy
 
• Requirement for inotropic or vasopressor support
 
• Intervention for complication of AP
 
• Alive and discharged at 30-days
 

Follow-up	30-days after admission.
Data collection period	1 July 2024 - 30 September 2024

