## 2. Aims

### Primary Aim:

To measure adherence with quality performance indicators (QPIs) for the management of AP during the first 72 hours after admission in AoNZ.

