## 3. Quality Performance Indicators

Multiple practice guidelines have been published for the management of AP (14–19). The recommendations in these guidelines are usually based on a systematic review of the relevant literature and the evidence on which is based on the available evidence, which is usually graded. Quality performance indicators will be drawn from these evidence-based recommendations for each of the nominated management domains that are relevant to the management of patients within the first 72 hours from admission to hospital. Any differences in the recommendations between the source guidelines will be resolved by discussion amongst the Scientific Advisory Group and consensus established for the QPIs.

The QPIs were developed for the following management domains: (Appendix D: Table 1 with guidelines)

**Table 1.** Quality Performance Indicators

	Domain	QPI	Ref*	Metrics
1	Diagnosis	All patients diagnosed within 12 hours of admission	IAP	RAC criteria for diagnosis: enzymes 3xUL, typical pain ± CT scan
2	Aetiology	All patients had tests for aetiology determined within 24 hours of admission	IAP	U/S for gallstones ETOH history with intake (units per week, timing of binge to pain) If both negative then lipids, IgG4, drugs
3	Severity (predicted)	All patients had prediction of severity on admission	IAP	N / Y, if yes method (drop-down of all options and other) Further drop-down bar will the give options for severity (mild, moderate, and severe)

4	Severity (actual)	All patients had actual severity determined at 48 hours	-	N / Y, if yes method (drop-down RAC, DBC and other) Further drop-down bar will the give options for severity (mild, moderate, and severe)
5	CT scan	Initial CT assessment performed after 72-96 hours if poor response to initial management or clinical deterioration, unless there is diagnostic uncertainty. Not required for severity prediction.	IAP	N / Y, if yes indication (drop-down with other)
6	Transfer	All patients with predicted or actual severe AP in the first 72 hours are discussed with specialist pancreas service.	Nice	N / Y Indication for transfer (drop-down)
7	Analgesia	All patients given narcotic analgesia within one hour of admission	-	Step-up or step-down approach? IV analgesia given on admission N / Y NSAIDS given to mild AP Analgesics prescribed

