## 4. Outcomes

### 4.1. Primary outcomes

- Proportion of patients that were managed in compliance with quality performance indicators overall

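### Excluding hypoxic patients who had no arterial blood gas selects the cohort on disease severity and on a local work-up decision

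*Protocol*

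**What the plan says.** Protocol 5.4 includes everyone aged 16 or over who presents to an acute public hospital with AP as defined in Appendix B. Its third exclusion then drops "Patients with suspected respiratory distress", marked by SpO2/FiO2 at or below 315, "who did not have an arterial blood gas test done to confirm respiratory failure". No time window and no reason are given.

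The primary aim in Section 2 is national: "To measure adherence with quality performance indicators (QPIs) for the management of AP during the first 72 hours after admission in AoNZ". Section 5.3 asks hospital leads to "capture all patients with AP that occur during the study inclusion period". The secondary aims compare outcomes within strata of AP severity. Section 4.2 lists ventilation, renal replacement, inotropic or vasopressor support and 30-day status as outcomes. Section 8 plans risk-adjusted funnel plots by hospital and multilevel models of outcome on compliance, and allows multiple imputation for missing data.

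Section 5.5 has no field for SpO2, FiO2 or a blood gas. It does record high-flow oxygen, non-invasive ventilation, mechanical ventilation and inotropes directly.

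**The concern.** The rule has two triggers. The first is low oxygenation, so only sicker patients can be removed. The second is that clinicians did not take a gas, which is a decision about work-up after presentation and can vary with hospital, team and resources. Removal therefore depends on severity and local practice jointly.

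Four parts of the plan are exposed:

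- The severity-stratified comparisons lose patients from the more severe strata.
- The ventilation and organ-support rates lose some of the patients most likely to have the outcome.
- The funnel plots compare hospitals whose retained patients were filtered differently. Risk adjustment cannot restore patients who were never entered.
- The multilevel outcome models use the same filtered cohort.

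Eligibility is fixed in the protocol, so this is not a matter left to a statistical analysis plan.

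**Working it through.** The protocol states no sample size, event rate or number excluded, so there is no figure to reproduce. The check has two parts.

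**1. Who is removed, and does the study need the gas?**

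| Patient | Gas taken | No gas |
|---|---|---|
| SpO2/FiO2 > 315 | kept | kept |
| SpO2/FiO2 ≤ 315 | kept | excluded |

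- The blood gas is in none of the 12 QPIs or their metrics (Table 1).
- No outcome in Section 4.2 and no field in Section 5.5 uses it.
- Appendix A (i) defines severity by organ failure and Appendix A (ii) defines renal failure. No gas-based respiratory criterion is given.
- The nearest link to measured care is QPI 4: "All patients had actual severity determined at 48 hours". A hypoxic patient whose respiratory failure was never confirmed might fail it, but the documents do not establish this.

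**2. How large could the effect be?** All rates below are assumptions except the 20% moderate-or-severe share, which is in Section 1.

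*Share excluded.* Let h be the hypoxic share and m the share of hypoxic patients with no gas. The excluded share is e = h × m.
- h = 5-15%, m = 20-60%: e = 1% to 9%.
- h = 10-20%, m = 30-50%: e = 3% to 10%. In an assumed 600 patients this is 18 to 60.

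*Share of the moderate-or-severe group.* If every excluded patient belonged to it, which is the extreme case, e = 1-9% would remove 0.01/0.20 = 5% to 0.09/0.20 = 45% of the group. Its observed share would fall from 20% to (0.20 − 0.01)/0.99 = 19.2%, or to (0.20 − 0.09)/0.91 = 12.1%.

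*Organ-support events lost*, with 18-60 excluded and an assumed 30 events in the full cohort:
- Risk without a gas 2-5%: 18 × 0.02 = 0.36 to 60 × 0.05 = 3.0 events, or 1.2% to 10%.
- Risk without a gas 15-20%, similar to other hypoxic patients: 18 × 0.15 = 2.7 to 60 × 0.20 = 12 events, or 9% to 40%.

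*Two hospitals with identical patients.* Take h = 10%, a ventilation risk of 15% across hypoxic patients and 0.5% in the rest. The true rate is 0.10 × 0.15 + 0.90 × 0.005 = 1.95% in both. If r is the risk in patients without a gas, the observed rate is (0.0195 − h·m·r)/(1 − h·m).

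| r | m = 10% | m = 60% | Gap (points) |
|---|---|---|---|
| 15% | 0.0180/0.99 = 1.82% | 0.0105/0.94 = 1.12% | 0.70 |
| 5% | 0.0190/0.99 = 1.92% | 0.0165/0.94 = 1.76% | 0.16 |
| 2% | 0.0193/0.99 = 1.95% | 0.0183/0.94 = 1.95% | about 0 |

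The rule alone can create a difference between hospitals. Its size depends almost entirely on r, which this dataset would not show.

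*Overall compliance.* Observed minus full-cohort compliance is e × (compliance in retained − compliance in excluded). With 60% in retained and 20-60% in excluded patients, e = 1-9% gives 0 to 0.09 × 40 = 3.6 points. If excluded patients were more compliant than the rest, the sign would reverse.

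**The case against.** The strongest defence is that the rule avoids patients whose respiratory failure, and hence severity class, cannot be confirmed. That is a plausible motive, although the protocol does not state it. It is, however, a missing-measurement problem and does not require removing the patient from every outcome.

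Several stronger readings are tempting but not supported:

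- *The primary result is inflated.* A reader might infer that the rule removes poorly managed patients and so raises overall compliance. The gas is not a QPI, and nothing in the protocol ties its omission to other gaps in care. Sicker patients could also be more compliant on some indicators.
- *Up to 40% of organ-support events are lost.* This gives patients who never had a gas the risk of other hypoxic patients or more. Gas-taking probably follows deterioration, so the group without one is likely to be at lower risk.
- *Patients become ineligible days after entry.* The missing time window permits this reading. Inclusion is worded around presentation, however, and the exclusion can be read the same way.
- *The exclusions cannot be counted.* They cannot be counted from the Section 5.5 fields, but they could be at screening. Section 8 commits to STROBE reporting, and other exclusions lack fields too.
- *The rule contradicts Section 5.3.* That text concerns finding patients under different teams, and any exclusion narrows a cohort. It shows the intended coverage and is not a contradiction.

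These points limit the claim about size and direction. They do not remove the selection itself.

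**Conclusion.** The concern holds as a design fault. The criterion selects on severity and on a work-up decision that can differ between hospitals, and no listed QPI or outcome needs the test. Its main reach is the severity-stratified comparisons, the ventilation and organ-support outcomes, and the hospital comparison.

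Under assumed rates it removes roughly 1-10% of patients. The loss of organ-support events is about 1-10% if those without a gas carry a 2-5% risk, and larger only if their risk is like that of other hypoxic patients. For the primary outcome, "Proportion of patients that were managed in compliance with quality performance indicators overall", an effect is possible, for example through QPI 4. The documents do not show its direction or size, and it may be near zero.

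**What to change.** - Delete the third exclusion in Protocol 5.4 and keep every patient who meets the Appendix B definition, subject to the other exclusions.
- Add to Section 5.5 the lowest SpO2/FiO2 and whether a blood gas was taken (yes/no, with value), and state the time window for each.
- Where no gas was taken, record respiratory failure as unconfirmed or missing. Handle it with the multiple imputation that Section 8 already allows, using SpO2/FiO2 and the recorded respiratory support as predictors. Do not use the 315 threshold to classify confirmed failure, because the protocol uses it only for suspected distress.
- Analyse ventilation and high-flow oxygen as already recorded. They need no gas.
- Report the number of unconfirmed patients per hospital, and apply the present exclusion only as a sensitivity analysis.

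The cost is protocol wording, two or three extra fields and some uncertainty in severity class for the flagged patients. Imputation assumes that a missing gas is explained by the recorded variables, and the sensitivity analysis shows how far the results depend on keeping these patients. Patient care is unchanged.
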